6.3 Type of control

The control group will consist of patients who follow the hypocaloric diet.

6.4 Masking Techniques

Not applicable. This is an open-label study

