One of the leading extra-hepatic causes of liver steatosis is metabolic syndrome (MS). Although, multiple definitions of MS exists; the essential components of MS include insulin resistance, increased levels of stress hormones, such as cortisol, and visceral obesity. In the obese population, the hallmarks of a metabolic syndrome are highly prevalent, being peripheral insulin resistance and increase levels of stress hormones the leading causes of organ injury. In such individuals higher levels of cortisol are expected, secondary to an over activated hypothalamic-pituitary-adrenal (HPA) (13, 14). A linear correlation between adrenal gland volume and metabolic syndrome has been demonstrated, with increased adrenal volume in patients under a metabolic syndrome status. However, once these patients are engaged on a treatment regime, leading to weight loss and diminished insulin resistance, the increase in adrenal volume tends to be reversible. Adrenal volume measurements can be achieved using cross-sectional imaging and semi-automated softwares. In clinical practice, adrenal gland dimensions are generally assessed using limb linear measurements on multidetector row computed tomography or magnetic resonance imaging (15,16).

We conducted a prospective longitudinal clinical study to correlate the effects of a very low-calorie-ketogenic diet (PRONOKAL method*), body weight loss and visceral fat reduction, with liver fat fraction, using a new MRI model of fat liver quantification (Ideal IQ**). Additionally, the degree of liver fat and its evolution, during the diet program, will be correlated with liver stiffness using MR Elastography. Adrenal gland measurements will also be made using the linear technique described by Carsin-Vu A. (16) to address its correlation with weight loss, visceral fat and liver steatosis.

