5 STUDY OBJECTIVES

5.1 Primary aim

- To evaluate the effects of body weight loss after a very low-calorie-ketogenic diet (Pronokal Method®) versus low calorie diet, on visceral fat reduction, liver fatty infiltration, using a new MRI technique of fat liver quantification (Ideal IQ**).

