7.5 Rationale of sample size

Exploratory pilot study to test a concept, where it has been estimated that 20 patients per group will be sufficient to analyze results.

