9 STUDY PROCEDURES AND OUTCOME MEASURES

9.1 Outcome measures

9.1.1 *Primary variables*

- Liver fatty infiltration, measured by a MRI technique of fat liver quantification (Ideal IQ**).
- Visceral fat, measured by the area in squared centimeters at the level of the 3rd vertebrae, using MRI technique.

9.1.2 *Secondary variable*

- Liver stiffness detected by MR Elastography
- Adrenal gland linear measurement
- Body weight
- Salivary cortisol levels

9.1.3 *End points*

- Reduction of fat infiltration into the liver between the baseline visit and 2 months (or end of the ketosis stage) and between the baseline visit and the control visit at month 6 of treatment.
- Visceral fat reduction between the baseline visit and 2 months (or end of the ketosis stage) and between the baseline visit and the control visit at month 6 of treatment.
- Correlation between degree of liver fat infiltration and liver stiffness
- Correlation between adrenal gland size and BMI, visceral fat and liver steatosis.
- Correlation between salivary cortisol levels and BMI, visceral fat and liver steatosis.
- Weight loss between the baseline visit and 2 months (or end of the ketosis stage) and between the baseline visit and the control visit at month 6 of treatment.

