9.2.2 Flow chart

	Pre-study	Onset	Visit at month 2 (end of ketosis)	Visit at month 6 (Final visit)
Review of inclusion and exclusion criteria.	X	X		
General blood test with liver function	X		X	X
Patient information	X			
Informed consent		X		
Comorbidities and medication		X	X	X
Anthropometric data (weight, BMI, WC)	X	X	X	X
MRI + MR Elastography		X	X	X
Salivary cortisol test		X	X	X
Adverse reactions			X	X
Drop outs and end of study			X	X

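### Section 6.4 sets masking aside because the diets are open-label, but the MR image readers could still be masked to arm, and the plan does not provide for it

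*Combined protocol and SAP*

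**What the plan says.** Section 6.4 consists of one statement: "Not applicable. This is an open-label study".

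Section 9.1 lists six variables, and four of them come from MR images. The two primary variables are liver fat, quantified by MRI with Ideal IQ, and visceral fat: "Visceral fat, measured by the area in squared centimeters at the level of the 3rd vertebrae, using MRI technique". Two secondary variables are "Liver stiffness detected by MR Elastography" and the adrenal linear measurement. On the last, section 4 says: "Adrenal gland measurements will also be made using the linear technique".

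The primary aim in section 5.1 compares the study diet "versus low calorie diet, on visceral fat reduction, liver fatty infiltration". The flow chart in section 9.2.2 schedules "MRI + MR Elastography" at onset, month 2 (end of ketosis) and month 6. Section 10.2 examines changes in liver fat, visceral fat and liver stiffness, both between visits and between groups. Adrenal size is not in that list and enters only the correlation analyses.

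Under section 13.1 the investigator checks the assigned group at the baseline visit, and the physician requests the MRI at that same visit. Section 1.15 mentions MR post-processing only as a cost covered by the grant, and says that the leading investigators do all the data analysis.

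**The concern.** Patients and staff who deliver a diet know which diet it is, but that does not stop someone else from reading coded images. Section 6.4 uses the first fact to dismiss masking altogether. The allocation is known at the visit where the first MRI is ordered, and the plan contains nothing to keep it from reaching the reader.

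If a reader knows the arm and this affects the reading, the shift adds to the between-group difference and cannot later be separated from a diet effect. Pilot status does not remove the problem, because the estimate itself is shifted whatever the true effect.

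Exposure differs by variable:
- **Visceral fat area (primary).** An area at one vertebral level may need slice choice and delineation, so this is the main concern.
- **Liver fat (primary).** Room for judgement may be small if quantification is automated. The plan does not say whether it is.
- **Liver stiffness (secondary).** It is compared between groups under section 10.2. The plan does not describe how it is read.
- **Adrenal linear measurement (secondary).** It is affected only through its planned correlations.

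**Working it through.** **Text check.** The places where reader masking could appear are section 1.15 (funding), 6.4 (masking), 9.2.1 and 9.2.2 (procedures and flow chart), 10.1 and 10.2 (analysis) and 13.1 (workplan). None says who reads the images, how each MR variable is derived, or whether the reader is kept unaware of the arm. The sections on sponsor, investigators and locations (1.2, 1.5 to 1.7, 3.5, 3.6) were not in the text available for review. Reader names could stand there; a masking rule is unlikely to.

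**Plan's own figure.** There is none to reproduce. Section 7.5 gives no effect size, SD or power, and no section gives a reading error.

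**Illustration.** Inputs:
- n = 20 per arm (section 7.4), all analysed (assumption).
- Significance level 0.05 (section 10.2), taken as two-sided (assumption).
- Two-sample t test on change, df = 20 + 20 − 2 = 38. This is an assumption: section 10.2 names Student's t in its paired form, which does not compare two groups.
- b = between-arm reading shift, in SD of change. Every value of b is an assumption.

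Formulas:
- Half-width of the 95% confidence interval = t(0.975; 38) × √(2/20) = 2.024 × 0.3162 = 0.640 SD.
- Share of the half-width = b / 0.640.
- False-positive rate with no true effect = probability that a noncentral t variable (38 df, noncentrality b / √(2/20) = b√10) lies outside ±2.024.
- Coverage of the true difference = 1 − that rate, at any true effect. It restates the same quantity and is not separate evidence.

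| Assumed b (SD) | Noncentrality | Share of half-width | False-positive rate | Coverage |
|---|---|---|---|---|
| 0 | 0 | 0% | 5.0% | 95.0% |
| 0.05 | 0.158 | 8% | 5.3% | 94.7% |
| 0.1 | 0.316 | 16% | 6.1% | 93.9% |
| 0.2 | 0.632 | 31% | 9.5% | 90.5% |
| 0.3 | 0.949 | 47% | 15.2% | 84.8% |

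A simulation (200,000 replicates; true effects of 0, 0.5 and 1.0 SD) gave coverage of 0.939, 0.904 to 0.906 and 0.848 to 0.849 for b = 0.1, 0.2 and 0.3. The bias equalled b to within 0.001 SD.

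The table applies to variables compared between groups. It does not describe the adrenal correlations.

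**Visit-related shifts.** Suppose knowing that a scan is a follow-up scan moves the reading by v in both arms. The between-group difference in change then moves by v − v = 0, but each within-group change moves by v. Section 10.2 tests both, so such a shift cancels in one comparison and not in the other.

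**Size of the task.** 40 patients × 3 MRI visits = at most 120 examinations.

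**The case against.** The strongest reply is that MR quantification leaves a reader little to decide. Section 9.1.1 names a quantification technique, section 4 explains that a fat fraction can be computed pixel by pixel, and section 1.15 refers to post-processing. This stands in part for liver fat. Section 4 is general background, however, and no section says that the trial's measurements are automated. It does not answer the point for visceral fat area.

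Second, this is a small study, described in section 7.5 as "Exploratory pilot study to test a concept", and the shifts in the table come from no document. That is right, and it limits how strongly the point can be put. If patients drop out (section 7.7), the interval widens and the inflation at a given b is smaller.

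Third, masking may fail. Section 4 reports more than 10% weight loss at 2 months in 96% of patients on this method, so visible fat loss may suggest the arm. Scan timing may do so too: under section 9.2.1 the ketogenic arm is scanned on reaching its weight-loss criterion or within 2 months, and the control arm at month 2. Both points stand. Removing dates deals with the second. The first means that masking may be incomplete, but it would still close the direct route through a label or request form.

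Two stronger readings are tempting and are not supported. A reader might infer that the images will be read with the arm known; the documents do not say so and only fail to provide the safeguard. A reader might also cite the adrenal measurement as the clearest case of a biased diet comparison, because a linear measurement leaves room for judgement. Section 10.2 plans no between-group comparison of adrenal size.

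**Conclusion.** The point holds as a cheap improvement. Section 6.4 dismisses masking for a reason that does not reach the image readers, and the rest of the available text does not make up for it. Both primary variables and liver stiffness are exposed in the between-group comparison, visceral fat area probably most. That ranking is a judgement, since the plan does not describe how any of them is measured.

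The size of the bias is unknown and may be near zero. The false-positive rates of 5.3% to 15.2% show only what assumed shifts of 0.05 to 0.3 SD would do with 20 per arm. A reader might take the upper figure as the trial's actual error rate; nothing in the documents supports that. Masked reading also would not address effects of the open-label diets on how patients and staff behave.

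**What to change.** Reword section 6.4 to say that the study is open-label for patients and treating staff, and that MRI and MR elastography outcomes are read masked to treatment arm. State who reads the images and how each MR variable is measured.

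Have existing staff who are not readers code the examinations with patient ID, arm and examination date removed, and have one of them hold the key. Lock the readings before linking them to allocation.

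Because section 10.2 also tests changes between visits, consider masking visit order for the operator-drawn measures. The price is the loss of side-by-side comparison with a patient's prior scans. Masking to arm alone keeps that comparison if a visit label replaces the date.

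The cost is a small coding task for at most 120 examinations, with no extra scans or patients. The documents neither cost this work nor confirm that such staff are available. Masking may remain incomplete where marked fat loss is visible.

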7 SUBJECT SELECTION

7.1 Study population

Obese patients of either sex with BMI over 30 kg/m², who agree to participate in the study.

7.2 Inclusion criteria:

- Patients of either sex, older than 18 years
-

-
- Obese patients with BMI equal or over 30kg/m²
 - Patients who agree to participate and sign the Informed Consent

7.3 Exclusion criteria:

- Pregnant or lactating women.
 - Patients weighing over 140 kg (by limitation of the MRI device)
 - Patients on anti-obesity drugs (eg, sibutramine, orlistat and liraglutide) or weight-interfering medications (eg, topiramate). In such cases a wash out period of 3 months is required.
 - Patients with alcohol intake > 20 g/day in women and > 30 g/day in men.
 - Patients with liver failure or with pathologies that may affect the liver
 - Patients with other causes of liver steatosis: chronic viral hepatitis and/or drug intake (corticosteroids, estrogens, NSAIDs, calcium antagonists, amiodarone, tamoxifen, tetracyclines, chloroquine, antiretrovirals, perhexiline).
 - Patients with eating disorders.
 - Patients with any psychiatric disorder (eg schizophrenia, bipolar disorder, substance abuse, severe depression).
 - Patients receiving dicumarinic anticoagulants (Sintrom®).
 - Patients taking corticosteroids.
 - Patients with severe kidney failure (gfr <30).
 - Patients with type 1 and type 2 diabetes mellitus.
 - Patients with hemopathies, including coagulation disorders
 - Patients with cardiovascular or cerebrovascular disease (of heart rate disorders, recent infarction [$<6m$], unstable angina, decompensated heart failure, recent stroke [$<6m$]).
 - Patients in acute attack of gout.
 - Patients with renal lithiasis verified by ultrasound.
 - Patients with cholelithiasis verified by ultrasound.
 - Patients with electrolyte imbalance, according to medical criteria.
 - Patients with orthostatic hypotension.
 - Patients with cancer or history of cancer who have not been discharged from oncology
 - Patients who are not expected to attend follow-up visits
-

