1.10 Condition in study

Fat infiltration into the liver (nonalcoholic fatty liver disease)

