9.2 Study procedures

9.2.1 *Follow-up of patients*

The patient follow-up will be 6 months. The patients will be visited monthly and data will be recorded on 4 occasions: pre-inclusion, baseline visit, final visit Active stage (end of ketosis) and visit at month 6.

Patients will be included after verifying the inclusion and exclusion criteria and after obtaining the signed informed consent.

Screening visit (day -15). In this visit, the patient's medical history will be assessed and a complete blood test will be required to verify the inclusion/exclusion criteria: complete blood count (red blood cells, leukocytes, neutrophils, hematocrit, hemoglobin), fasting blood glucose, Hb1c, insulinemia, lipid profile (total cholesterol, c-HDL, c-LDL, triglycerides), kidney function (serum creatinine, creatinine clearance, glomerular filtration), nitrogen balance (urea, uric acid), thyroid profile (TSH, T4) and ionogram (Na, K, Cl, Ca, Mg)

The pre-inclusion blood test will also include liver function tests as the first screening of hepatic steatosis:

- GOT
- GPT
- Gamma-GT
- Bilirubin
- Albumin
- Prothrombin time
- Ferritin
- Alkaline phosphatase.

In addition, the patients will be informed about the study through the patient information sheet (Attachment 1) and they will be provided with an informed consent (Attachment 2).

At the baseline visit (day 0). The results of the additional tests (blood tests) will be verified to complete the inclusion/exclusion criteria.

Liver function data will be reviewed. Patients with one or more of the following conditions will be considered as suspicious of hepatic steatosis:

- GPT/GOT ratio over 1
- Gamma-GT and alkaline phosphatase increased twice to three times the normal levels
- High ferritin
- Normal bilirubin and albumin in the presence of any of the above changes

The informed consent will be signed and randomized. The corresponding diet will be scheduled depending on the treatment group (VLCK diet group or control group) and the physical exercise program. Patient demographics (sex, age, weight, height, comorbidities and medication) will be recorded. Anthropometric data (weight, BMI, waist circumference) will be recorded. Fat infiltration into liver and visceral fat will be scanned by MRI and hepatic stiffness will be assessed by MR Elastography. The salivary cortisol levels will also be tested.

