13 PRACTICAL CONSIDERATIONS

13.1 Workplan

The investigators will be in charge of recruiting patients. Once the patients have confirmed their willingness to participate in the study, the investigator should verify if they meet the inclusion/exclusion criteria of this study. If they are eligible, they will be requested the additional tests (blood test with liver function) and will be informed on every issue of the study through the Patient Information Sheet (Attachment 1).

At the baseline visit, once the complementary tests have been reviewed and verified to meet inclusion criteria, the physician must confirm that the patient agrees to participate in the study and obtain the patient's signature of the Informed Consent (Attachment 2). Upon signing, the investigator will verify the assigned group according to the randomization list.

At this baseline visit, the physician should request MRI and MR Elastography to assess the degree of hepatic steatosis, the amount of visceral fat and liver stiffness. The physician will also perform the first salivary cortisol test on the patient. Also, he should record the clinical data requested in the Data Collection Notebook and schedule the treatment.

During the weight loss treatment, patients in the study group will be monitored by the investigator fortnightly during the protein diet (Ketogenic Active Stage), although at these additional visits no data are expected to be collected for the study. Upon completion of the first two months of follow-up, the study group will end the ketogenic stage and from that moment on, the patients will be controlled outside the center by dietitians specialized in the Pronokal® Method. Patients in the control group (hypocaloric diet) will undergo controls at the center monthly, although data will only be recorded in the visits arranged in this protocol (screening, baseline, month2 and month 6).

At the moment the patient completes the two months of follow-up, the data requested in the DCN will be recorded, the salivary cortisol test will be performed and an MRI and a MR Elastography will be requested.

The investigator, apart from monthly visits or any additional visits deemed necessary, will have an appointment with the patient at month 6 of treatment for a new clinical assessment, will record the anthropometric data, and request a Control MRI and MR Elastography.

At the end of the 6-month follow-up, the study will be completed.

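### Baseline MRI liver fat is collected in every patient but not used to select, stratify, adjust or define a subset, so the between-arm test of liver-fat change loses precision and may be diluted

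*Combined protocol and SAP*

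**What the plan says.** Section 1.10 gives fatty infiltration of the liver as the condition under study. Section 9.1.1 lists two primary variables: MRI liver fat, and "Visceral fat, measured by the area in squared centimeters at the level of the 3rd vertebrae, using MRI technique".

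Section 7.2 admits adults who consent and who are "Obese patients with BMI equal or over 30kg/m²". The exclusions in 7.3 remove alcohol, viral and drug causes of steatosis, but no criterion requires steatosis to be present.

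Section 9.2.1 states: "The pre-inclusion blood test will also include liver function tests as the first screening of hepatic steatosis". At the baseline visit, patients with any of the listed laboratory findings "will be considered as suspicious of hepatic steatosis". No rule on entry, stratification or analysis follows from that label.

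On timing, section 13.1 says: "Upon signing, the investigator will verify the assigned group according to the randomization list". The MRI request is described after that step, with no threshold. Section 6.2 names no stratification factor.

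The baseline scan does enter the analysis. Section 9.1.3 defines the liver-fat endpoints as reductions from baseline to the end of ketosis (2 months) and to month 6, and 10.2 compares these changes between visits and between groups. The named tests are Student's t and Mann–Whitney, with no covariate, stratum or steatosis subset. Section 7.5 describes an exploratory pilot and gives no power, effect size or SD.

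**The concern.** A patient whose liver fat is already low has little to lose on either diet. Section 10.2 gives that patient the same weight as one with marked steatosis. There are three possible consequences for the liver-fat comparison:

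- The spread of baseline values feeds into the spread of changes and widens the interval.
- With 20 per arm and no stratification, the arms can differ by chance in how much fat there was to lose, and an unadjusted test of change does not correct for that.
- If a material share of entrants cannot respond, the average difference is smaller than the difference among patients who have the named condition.

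The first two can be addressed with data already being collected. The third also affects wording: a result averaged over everyone with obesity does not directly describe patients with fatty liver disease.

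**Working it through.** **Inputs from the documents.** 20 patients per arm (7.4), 1:1 allocation (6.2), significance level 0.05 (10.2). Sidedness is not stated; two-sided is assumed.

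**Inputs the documents do not give (assumptions).** The share *s* of entrants with liver fat to lose, the effect and SD in those patients, and the correlation *r* between baseline liver fat and its change.

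**1. Reference effect.** The planned 20 per arm cannot be reproduced, because 7.5 gives nothing to reproduce it from. As a yardstick only, the standardized difference detectable with 80% power is

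d₀ = (1.960 + 0.842) × √(2/20) = 2.802 × 0.316 = 0.886 SD.

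A t-based calculation gives 0.91 SD and the same powers below.

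**2. Possible dilution.** If a share *s* has effect d₀ and the rest have none, with the same SD, the overall effect is s × d₀ and power is Φ(s × d₀/√(2/20) − 1.960).

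| s | Overall effect (SD) | Power at 20 per arm |
|---|---|---|
| 1.0 | 0.886 | 80% |
| 0.9 | 0.797 | 71% |
| 0.8 | 0.709 | 61% |
| 0.7 | 0.620 | 50% |
| 0.6 | 0.532 | 39% |
| 0.5 | 0.443 | 29% |

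The equal-SD assumption is not critical. Suppose mean falls of 10 and 5 points with SD 5.64 in steatotic patients, and no change with SD 1 in the others (all assumed). With the mixture SD, power is 80% at s = 1.0, 56% at 0.8 and 29% at 0.5.

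**3. Chance imbalance.** Treat the number of steatotic patients in each arm as binomial (20, s). The chance that the arms differ by four or more is about 27% at s = 0.5, 23% at 0.7, 16% at 0.8 and 6% at 0.9.

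**4. What adjustment gains.** Adjusting for baseline multiplies the residual variance by 1 − r².

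- r = 0.4: 1 − 0.16 = 0.84, so 16% is removed, equivalent to 20/0.84 = 23.8 per arm unadjusted.
- r = 0.7: 1 − 0.49 = 0.51, so 49% is removed (the remaining factor is 51%), equivalent to 20/0.51 = 39.2 per arm.

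The reduction is therefore 16–49%; the 51% at the upper end is the share that remains.

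**5. What adjustment does not do.** Randomized arms with a main-effect covariate still estimate the average effect over all entrants, s × d₀. The interval narrows but the target does not move.

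**6. What the subset gives.** Under the same assumptions the subset has 20s per arm and the full effect d₀.

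- s = 0.8, 16 per arm: 0.886/√(2/16) = 2.506, power about 71%, against 61% for the whole group. The 95% interval half-width is 1.96 × √(2/16) = 0.69 SD.
- s = 0.5, 10 per arm: 0.886/√(2/10) = 1.981, power about 51%, against 29%. The half-width is 1.96 × √(2/10) = 0.88 SD.

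For all 20 per arm the half-width is 1.96 × √(2/20) = 0.62 SD. The subset does better than the diluted comparison but does not restore 80%.

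**The case against.** Enrolling by BMI is defensible. Sections 1.13 and 7.1 define the population as obese patients, visceral fat needs no steatosis, and the correlation aims in 5.2 benefit from a wide range of liver fat. The trial is an exploratory pilot that claims no power, so none of the figures above contradicts a stated one. All of this stands, and it is why eligibility should not be changed.

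Three stronger readings are tempting, and the documents do not support them:

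- A reader might infer that the baseline MRI is left out of the analysis. It is not: it anchors every change in 9.1.3 and 10.2, and the dropout rule in 7.7 depends on it.
- A reader might infer that the effect is diluted as a matter of fact. No prevalence is given, fat fraction is continuous, and a low value can still fall, so zero response in 20–50% of entrants is a severe assumption.
- A reader might infer that a null result could never be distinguished from a floor effect. Baseline liver fat is measured in everyone and 10.1 describes all collected variables, so a low baseline would be visible.

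None of this answers the remaining point: the between-group test in 10.2 ignores a baseline measurement of the same quantity, available for every patient.

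**Conclusion.** The point holds for the liver-fat comparison. Steatosis is not required, the laboratory flag has no stated consequence, and baseline liver fat serves as the reference for change but not to select, stratify, adjust or define a subset.

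The loss of precision and the exposure to chance imbalance follow from the stated method. Their size depends on an unknown correlation: at 0.4–0.7, the residual variance would be 84–51% of its unadjusted value. Dilution is a possible risk, not an established one. The fall from 80% to about 61–29% rests on an assumed 20–50% of non-responders and on an effect chosen to give 80% power at 20 per arm. It shows sensitivity and does not estimate this trial's power. Visceral fat is outside the point.

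**What to change.** Leave eligibility, visits and scans unchanged.

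1. In 10.2, replace the between-group test of liver-fat change with ANCOVA at each follow-up time, with baseline MRI fat fraction as covariate. Report the adjusted difference with its 95% interval. State that this improves precision and corrects baseline imbalance, and that it does not remove dilution.
2. To address dilution, add one supportive between-arm contrast in patients with steatosis on the baseline MRI. Fix the fat-fraction threshold before any outcome data are seen, and report the result with its interval as exploratory.
3. State the conclusions for adults with obesity.
4. As a minor point, say in 9.2.1 what the laboratory flag is for, or remove it.

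The cost is a change of analysis wording and one extra analysis. The downside is that the steatosis subset is small (16 or 10 per arm in the examples above), so its interval will be wide.
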